5.5 Pharmacokinetic, Pharmacodynamic, Pharmacogenomic, and Other Biomarker Analyses

5.5.1 Pharmacokinetic Analyses

Individual listings with a summary of plasma concentrations of lenvatinib and a figure containing lenvatinib plasma concentrations versus PK sampling time will be provided by subject and lenvatinib starting dose (18 vs 24 mg) for subjects in the Pharmacokinetic Analysis Set. Other PK analyses will be described in a separate SAP for PK/PD/Biomarkers.

5.5.2 Pharmacodynamic, Pharmacogenomic, and Other Biomarker Analyses

Summary of TSH, thyroglobulin (Tg), anti-Tg antibodies and other serum biomarkers (including VEGF, Ang-2, sTie-2, FGF23) will be provided by visit using Safety Analysis Set. Listings and Box and Whisker plots of serum pharmacodynamic results over time and the figure for the percentage change from Baseline for serum pharmacodynamic results over time will be provided.

Other pharmacodynamic and biomarker analyses will be described in a separate SAP for PK/PD/Biomarker.

5.6 Safety Analyses

All safety analyses will be performed on the Safety Analysis Set. Safety data, presented by the starting lenvatinib dose of 24 mg or 18 mg and overall will be summarized on an “as treated” basis using descriptive statistics (i.e., n, mean, standard deviation, median, minimum, and maximum values for continuous variables; n [%] for categorical variables). Safety variables include TEAEs, TEAEs with CTCAE Grade ≥ 3 , intolerable TEAEs of CTCAE Grade 2 (based on data collected in CRF), treatment-related TEAEs, treatment-emergent serious adverse events (SAEs), clinical laboratory parameters, vital signs, 12-lead ECG results, ECOG PS scores, and left ventricular ejection fraction (LVEF). Abnormal values will be flagged.

Study Day 1 for all safety analyses is defined as the date of the first dose of study drug.

5.6.1 Extent of Exposure

Treatment period consisted of 28-day blinded study treatment cycles (i.e., 1 to 28 days per cycle) (Section 3.2). Per protocol, subjects received 1 of the 2 starting doses, lenvatinib 24 mg/day or lenvatinib 18 mg/day. Dose reductions would occur in succession based on the subject's previous dose level (24, 20, 14, 10, and 8 mg QD, or 18, 14, 10, 8, and 4 mg QD, respectively).

The following analyses will be performed:

- Duration of Treatment (months): $(\text{last dose date} - \text{first dose date} + 1) / (365.25/12)$
- Number of Subject-months: sum of treatment time (in months) for all subjects (including dose interruption).
- Total dose (mg) taken per subject
- Dose intensity (mg/day) per subject (i.e., total dose/treatment duration), relative dose intensity (%) per subject (i.e., percentage of dose intensity relative to the planned dose at Baseline)
- Dose modification (reduction, interruption), frequency of dose modification
- Treatment discontinuation due to AE (from treatment disposition page)
- Time to first dose reduction (weeks), time to treatment discontinuation due to AE (weeks). Both will be analyzed using KM method (same as for PFS, see Section 5.4.1) and estimated quartiles and the 95% CI will be presented.

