#### 9.5.4 Discontinuation of Subjects

A subject may elect to discontinue the study at any time for any reason. Subjects who choose to discontinue study drug prior to disease progression will be followed in the poststudy treatment follow-up period and continue to undergo regularly scheduled disease assessment until documentation of disease progression or initiation of alternative anticancer treatment. All subjects who discontinue study drug will be followed for PFS2 and OS, and all postprogression cancer treatments administered will be recorded. Subjects may at any time withdraw consent for further study participation. No further data will be collected on subjects once consent has been withdrawn. All subjects who discontinue the study are to complete the study's early discontinuation procedures indicated in the Schedule of Procedures and Assessments (Table 7).

The investigator will promptly explain to the subject involved that the study will be discontinued for that subject and provide appropriate medical treatment and other necessary measures for the subject. A subject who has ceased to return for visits will be followed up by mail, phone, or other means to gather information such as the reason for failure to return, the status of treatment compliance, the presence or absence of AEs, and clinical courses of signs and symptoms.

Subjects who discontinue early from the study will be discontinued for one of these primary reasons: AE(s), lost to follow-up, subject choice, progressive disease, or administrative/other. In addition to the primary reason, the subject may indicate one or more secondary reason(s) for discontinuation. Study disposition information will be collected on the Subject Disposition CRF.

A subject removed from the study for any reason may not be replaced.

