#### 9.7.1.1.2 SECONDARY ENDPOINTS

- PFS, defined as the time from the date of randomization to the date of first documentation of disease progression, or date of death, whichever occurs first. Censoring rules for PFS will be defined in the SAP and will follow FDA guidance.
- PFS2, defined as the time from randomization to second objective disease progression (occurring during treatment with next line of anticancer therapy), or death from any cause, whichever occurs first. Censoring rules for PFS2 will be defined in the SAP.
- Overall safety profile and tolerability.
- Time to treatment discontinuation due to an AE.
- Number of dose reductions.
- Time to first dose reduction.
- Plasma PK lenvatinib exposure parameters.
- Interrelationships of lenvatinib exposure, changes in thyroglobulin, TSH, or other exploratory serum biomarkers, and changes in tumor burden and PFS.
- Relationship of lenvatinib exposure and changes in BP, and AEs of weight loss, fatigue, nausea, vomiting, diarrhea, and proteinuria CTCAE grades derived from urine protein measurements.
- Impact of lenvatinib treatment on HRQoL as assessed using the validated instruments EQ-5D-3L and FACT-G.

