5.1.2 Secondary Endpoints

- PFS, defined as the time from the date of randomization to the date of first documentation of disease progression, or date of death, whichever occurs first
- PFS2, defined as the time from randomization to second objective disease progression (occurring during treatment with next line of anticancer therapy), or death from any cause, whichever occurs first
- Overall safety profile and tolerability
- Time to treatment discontinuation due to an adverse event (AE)
- Number of dose reductions

- Time to first dose reduction
 - *Plasma PK lenvatinib exposure parameters
 - *Interrelationships of lenvatinib exposure, changes in thyroglobulin, TSH, or other exploratory serum biomarkers, and changes in tumor burden and PFS
 - *Relationship of lenvatinib exposure and changes in blood pressure (BP), and AEs of weight loss, fatigue, nausea, vomiting, diarrhea, and proteinuria CTCAE grades derived from urine protein measurements
 - *Impact of lenvatinib treatment on HRQoL as assessed using the validated instruments EQ-5D-3L and FACT-G
- * Will be provided in separate reports.

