5.3.5 Handling of Missing Data, Dropouts, and Outliers

Rules for handling full/partial missing dates, and the censoring rules for PFS, PFS2, and OS are explained in [Section 8.4](#). The handling of missing data in the analyses of ORR, CBR and

DCR is explained in Sections 5.4. Any potential outlier values will be investigated and will be analyzed in the locked database as originally reported.

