8.4 Censoring Rules

The censoring rules for PFS are explained in [Table 4](#), based upon investigator's tumor assessments and the FDA Guidance for Industry, *Clinical Trial Endpoints for the Approval of Cancer Drugs and Biologics* (2007).

For PFS2, if a subject did not have PD (solely based on the investigator-provided information on the Survival Status eCRF) after starting a new anticancer treatment, or did not die during the study, the subject will be censored on the date last known to be alive.

For OS, in the absence of confirmation of death, subjects will be censored either at the date last known to be alive or the date of data cutoff, whichever is earlier.

Table 4 Censoring Rules for Progression-Free Survival

No.	Situation	Date of Progression or Censoring	Outcome
1	No baseline or postbaseline tumor assessments	Date of randomization	Censored
2	Progression documented between scheduled visits	Date of first radiologic PD assessment	Progressed
3	No progression at the time of data cutoff	Date of last adequate radiologic assessment prior to or on date of data cutoff	Censored
4	New anticancer treatment started	Date of last adequate radiologic assessment prior to or on date of new anticancer treatment	Censored
5	Death before first PD assessment	Date of death	Progressed
6	Death between adequate assessment visits*	Date of death	Progressed
7	Death or progression after more than one missed visit** or after 28 days from the last dose of study treatment	Date of last adequate radiologic assessment before missed tumor assessments	Censored
8	Treatment discontinuation for reasons other than PD	Date of last radiologic assessment before treatment discontinuation	Censored

CR = complete response, PD = progressive disease, PR = partial response, SD = stable disease.

* Adequate tumor assessment is a radiologic assessment of CR, PR, SD, non-CR/non-PD or PD as determined by investigators.

** More than 1 missed visits is defined as having either 1 of the following 2 durations being longer than 18 weeks - 1 day, which is 125 days ($= ((8+1) \times 2 \times 7) - 1$) for subjects on the every-8-week tumor assessment schedule in this study:

- a. Duration between 2 consecutive tumor assessments
- b. Duration between the last adequate tumor assessment and death or PD

The priority of the censoring rules is as follows:

1. If the subject had PD or death, the following sequence will be applied:

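### SAP 5.6.1 gives no event or censoring rule for time to AE discontinuation and time to first dose reduction, and plain Kaplan-Meier is likely to overstate the long-term risk of AE discontinuation

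*SAP*

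**What the plan says.** Protocol Section 9.7.1.1.2 lists "Time to treatment discontinuation due to an AE" and time to first dose reduction as secondary endpoints, and SAP Section 5.1.2 repeats them. Protocol Section 9.7.1.8 says only that they will be summarised. The method is in SAP Section 5.6.1: "Both will be analyzed using KM method". The same sentence equates this with the PFS method, cites Section 5.4.1, and asks for quartiles with 95% CIs.

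SAP Section 5.3.5 says that "the censoring rules for PFS, PFS2, and OS are explained in" Section 8.4. That section covers PFS, PFS2 and OS and neither of these two endpoints.

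Protocol Section 9.5.4 lists the primary reasons for early discontinuation as "AE(s), lost to follow-up, subject choice, progressive disease, or administrative/other". Neither document mentions competing risks or cumulative incidence.

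Other summaries of the same events are planned. SAP Section 5.6.1 tabulates AE discontinuation from the disposition page and dose modifications. Section 5.6.2 gives n (%) for TEAEs leading to discontinuation and to dose reduction or interruption. Section 5.2.2 summarises the primary reason for discontinuation.

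**The concern.** A programmer cannot derive either endpoint from the text. The reference leads to a response-rate analysis, and the PFS rules do not fit.

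There is also a question of method. A subject who has stopped for progression, or has died, can no longer stop for an AE or have a dose reduced. If such subjects are censored, Kaplan-Meier drops them from the risk set and assumes that they would have gone on to have the event at the same rate as those still treated. One minus Kaplan-Meier is then the risk in a setting where nobody stops for any other reason. It is higher than the proportion of randomised subjects who actually stop for an AE, and the planned quartiles are correspondingly early. These endpoints help to describe tolerability in a trial that asks whether 18 mg has a better safety profile than 24 mg, so a reader is likely to take the curves as real probabilities.

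**Working it through.** **1. Can the PFS rules be used?** Set side by side, they cannot.
- SAP Section 5.4.1 analyses ORR at Week 24. The Kaplan-Meier methods for PFS are in Section 5.4.2.
- SAP Table 4 counts progression and death as events. For AE discontinuation both are competing events.
- Row 8 of Table 4 censors "Treatment discontinuation for reasons other than PD". That includes stopping for an AE, which is the event to be measured.

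**2. Inputs for the size.** The documents give no figure for AE discontinuation over time, so there is nothing of the plan's own to reproduce.
- Competing hazard: Study 303 median PFS at 24 mg is 18.3 months (Protocol Section 7.1). With a constant hazard, c = ln 2 / 18.3 = 0.0379 per month.
- AE-discontinuation hazard a: an assumption, 0.015 per month with a range of 0.008 to 0.025.
- Week 24 = 168 / 30.4375 = 5.52 months. Time on treatment may range from 6 to 42 months (Protocol synopsis).

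**3. Formulas, with progression and death censored in Kaplan-Meier.**
- One minus Kaplan-Meier: 1 − exp(−a t).
- Cumulative incidence: a/(a+c) × [1 − exp(−(a+c) t)].
- Worked case, a = 0.015 and t = 24: Kaplan-Meier 1 − exp(−0.36) = 30.2%. Cumulative incidence 0.015/0.0529 × [1 − exp(−1.269)] = 0.284 × 0.719 = 20.4%.

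| a per month | Week 24, KM vs CIF | 24 months, KM vs CIF | First quartile, KM vs CIF |
|---|---|---|---|
| 0.008 | 4.3% vs 3.9% | 17.5% vs 11.6% | 36.0 months vs never reached |
| 0.015 | 7.9% vs 7.2% | 30.2% vs 20.4% | 19.2 vs 40.3 months |
| 0.025 | 12.9% vs 11.7% | 45.1% vs 31.0% | 11.5 vs 15.8 months |

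The overstatement at 24 months is about 1.5-fold, and at Week 24 it is 0.4 to 1.2 points. At a = 0.025 Kaplan-Meier gives a median of ln 2 / 0.025 = 27.7 months. Yet at most 0.025/0.0629 = 40% of subjects would ever stop for an AE, so no median exists.

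**4. Time to first dose reduction.** Protocol Section 7.1 gives a median of 3 months among Study 303 subjects who needed a reduction. Taking 3 months as the Kaplan-Meier median is an assumption: a = ln 2 / 3 = 0.231. With the same c, Kaplan-Meier and cumulative incidence give a first quartile of 1.25 vs 1.28 months, a median of 3.0 vs 3.2, and a third quartile of 6.0 vs 7.7.

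**5. Between doses.** Take a = 0.015 in the 24 mg arm. The 24-month difference, 18 mg minus 24 mg, in points is as follows.

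| AE hazard ratio | Progression hazard ratio | KM | CIF |
|---|---|---|---|
| 1 | 1 | 0.0 | 0.0 |
| 0.75 | 1 | −6.6 | −4.5 |
| 0.75 | 2 | −6.6 | −9.1 |
| 1 | 1.5 | 0.0 | −3.2 |
| 1.15 | 1.5 | +3.7 | −1.0 |

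The hazard ratios are illustrative. Kaplan-Meier can show a larger or a smaller difference than cumulative incidence.

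**The case against.** The strongest reply is that the SAP nowhere says that progression and death will be censored. That is correct. A reader might infer a stated censoring rule from the words about Kaplan-Meier, but the documents contain none. What can be shown from the text is that the rule is missing and the reference is wrong. The overstatement in the working is what follows from the usual implementation.

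A second tempting reading is that Kaplan-Meier hides true dose differences and cumulative incidence reveals them. The last two rows of the dose table show why that does not stand. With equal AE hazards and faster progression on 18 mg, Kaplan-Meier correctly shows no difference in AE hazard. Cumulative incidence favours 18 mg by 3.2 points only because subjects left through progression. With a 15% higher AE hazard on 18 mg, cumulative incidence would still favour it by 1.0 point. The two estimates answer different questions, so replacing one with the other is not justified.

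A third is that the safety conclusion itself is at risk. The primary objective rests on Grade 3 or higher TEAEs in the first 24 weeks, which SAP Section 5.6.2 analyses as a crude difference in proportions. Section 5.6.1 names no between-arm test for the two time-to-event endpoints. The crude counts of AE discontinuation and the reasons for stopping are also planned, although they give no timing.

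It is also fair to say that the size depends on an assumed AE hazard. In addition, the competing hazard comes from independent-review PFS in another study, while this trial uses investigator assessment.

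**Conclusion.** The point holds in limited form. Section 5.6.1 does not define the event or the censoring for two secondary endpoints, points to the wrong section, and cannot borrow Table 4. If other stops and death are censored, the long-term probability of AE discontinuation is overstated and its quartiles come early. The 24-month gap is about 6 points (17.5 − 11.6) to 14 points (45.1 − 31.0) over the assumed range, and about 1 point at Week 24. For first dose reduction only the third quartile moves noticeably.

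These sizes rest on constant hazards, an assumed AE hazard, and a competing hazard that covers progression and death only. Stops by subject choice or for administrative reasons would add to it. Any effect on the dose contrast depends on whether progression differs by arm, and can go either way. The primary safety endpoint is untouched. This is an inexpensive improvement to a descriptive secondary analysis and no threat to the trial's main conclusion.

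**What to change.** In SAP Section 5.6.1, before database lock:
- For each of the two endpoints, define the event, the competing events (discontinuation for any other reason, and death) and the censoring (data cutoff).
- Correct the reference from Section 5.4.1 to 5.4.2, and say that the censoring rules of Table 4 do not apply.
- Add Aalen-Johansen cumulative incidence by arm with 95% CIs at 24 weeks, 12 months and 24 months. Take absolute risks and quartiles from it, reporting a quartile as not reached where that is so.
- Keep Kaplan-Meier alongside as the view of the cause-specific hazard, and show reasons for discontinuation by arm next to both.

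The reasons for stopping are already collected, so the cost is a short SAP edit and a little programming. The drawback is slightly more analysis, and two estimates that have to be read together.

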5.6.2 Adverse Events

The AE verbatim descriptions (investigator terms from the CRF) will be classified into standardized medical terminology using the MedDRA. Adverse events will be coded to MedDRA (version 23.0) lower level term (LLT) closest to the verbatim term. The linked

MedDRA PT and primary SOC will also be captured in the database. The CTCAE grading (version 4.03) will be included in the database.

A TEAE is defined as an AE that emerged during treatment (from time of first dose up to 28 days following the last dose of study drug), having been absent pretreatment (Baseline) or

- Reemerged during treatment, having been present pretreatment (Baseline) but stopped before treatment, or
- Worsened in severity during treatment relative to the pretreatment state, when the AE was continuous

Only TEAEs will be summarized. A subject will be counted only once within each category (i.e., SOC, PT, worst grade, or other specific category to be summarized in table) even if the subject experienced more than 1 TEAE within the category. All AEs, treatment-emergent or otherwise, will be presented in subject data listings.

For the analysis of the primary safety endpoint of rate of TEAEs with CTCAE Grade ≥ 3 within 24 weeks after randomization (as of the Week 24 time point), the number (percentage) of subjects with TEAEs of CTCAE Grade ≥ 3 as of Week 24 will be reported; the difference in frequency between the treatments (18 mg minus 24 mg) will be presented with 95% CI, using asymptotic normal approximation. In addition, the number (percentage) of subjects with TEAEs with CTCAE Grade ≥ 3 as of the Week 24 will be summarized by SOC and PT.

The incidence of TEAEs will be reported as the number (percentage) of subjects with TEAEs by SOC, PT and worst CTCAE grade. The number (percentage) of subjects with TEAEs will also be summarized by PT and worst CTCAE grade.

The number (percentage) of subjects with treatment-related TEAEs, TEAEs leading to treatment discontinuation, TEAEs leading to dose reduction/interruption, will be summarized by SOC, PT and worst CTCAE grade. All SAEs, treatment-related SAEs, fatal TEAEs, and nonfatal SAEs will be summarized by SOC and PT. Treatment-related TEAEs include those events considered by the investigator to be related to study treatment or TEAEs with a missing causality on the CRF.

In addition, summaries of clinically significant TEAEs (CSEs) (i.e., subject incidence, time to first onset of Grade 3 or 4) will be provided. [Appendix 13.2](#) includes the list of CSEs. These CSEs include those AEs known to be of concern with lenvatinib or of VEGF-targeted agents in general.

TEAEs, SAEs, treatment-related TEAEs, treatment-related SAEs, CSEs will also be summarized by PT in decreasing frequency.

The number (percentage) of subjects with all deaths and deaths on treatment or within 30 days of last lenvatinib dose will be summarized.

Subject data listings for (1) all AEs, (2) AEs of CTCAE Grade 2 (intolerable) or above, (3) serious adverse events, (4) fatal AEs, (5) all deaths, (6) AEs leading to treatment discontinuation, and (7) AEs leading to dose reduction or interruption will be provided.

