#### **Analyses of Primary Endpoint:**

The analysis of ORR24wk will be based on a noninferiority test on the odds ratio (OR) and will be tested with a noninferiority margin of 0.4 on an OR scale (see **Sample Size Rationale** for the margin estimation) and a 1-sided alpha of 0.025. The point estimate of ORR24wk for each treatment group (24 mg and 18 mg) will be summarized with corresponding 95% confidence interval (CI). Treatment differences in ORR24w for the 24-mg and 18-mg dose groups will be estimated along with 95% CIs based on the normal approximation. The OR of ORR24wk (18 mg vs 24 mg) along with the 95% CI will be calculated using the Cochran-Mantel-Haenszel (CMH) method stratified by ECOG PS (0 vs 1 or 2) and age group ( $\leq 65$  or  $>65$  years).

The overall ORR will also be analyzed according to the same approach for ORR24wk as a sensitivity analysis.

For the analysis of the primary safety endpoint, frequency (number and percentage) will be summarized for TEAEs with a CTCAE grade of 3 or higher by treatment (24 mg and 18 mg), and the difference in the frequency between the 2 treatment groups will also be presented with 95% CI.

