### 9.4.3 Method of Assigning Subjects to Treatment Groups

Subjects will be randomized in a 1:1 ratio to receive lenvatinib 24 mg or 18 mg QD based on a computer-generated randomization scheme that will be reviewed and approved by an independent statistician. Subjects will be stratified by age ( $\leq 65$  years or  $>65$  years) and ECOG PS of 0 versus 1 or 2.

The randomization scheme and identification for each subject will be included in the final CSR for this study.

Randomization will be performed centrally by an interactive voice and web response system (IxRS). The IxRS or clinical supply vendor will generate the randomized blister card identification numbers. At enrollment (and after successful completion of Visit 1), the investigator or designee will call/log into the IxRS to register the subject information. At randomization (Visit 2), the IxRS will assign each subject a unique 6-digit randomization number. To dispense every subsequent carton (or 2 cartons), the investigator or a designee will call/log into the IxRS to obtain dispensing instructions and register the subject's visit and whether the same or a reduced dose should be dispensed.

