##### 9.7.1.8.1 PRIMARY SAFETY ENDPOINT

For the analysis of the primary safety endpoint, the frequency (number and percentage) of TEAEs with CTCAE grade of 3 or higher will be summarized by treatment group (24 mg and 18 mg); the difference in the frequency between the 2 treatment groups will be presented with 95% CI.

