3.2 Overall Study Design and Plan

This was a multicenter, randomized, double-blind study being conducted as a postmarketing commitment to the US Food and Drug Administration (FDA) and the European Medicines Agency (EMA) to evaluate whether there was a lower starting dosage of lenvatinib other than 24 mg QD that could provide comparable efficacy but have a better safety profile in subjects with RR-DTC with radiographic evidence of disease progression (PD) within the prior 12 months.

Eligible subjects should have measurable disease according to Response Evaluation Criteria in Solid Tumors Version 1.1 (RECIST 1.1) and evidence of PD within 13 months before signing informed consent (both assessed by independent radiologic review) and were randomly assigned to treatment in a 1:1 ratio to receive lenvatinib 24 mg or 18 mg orally QD. The total sample size is 152 subjects (76 subjects per arm). Randomization was stratified by age (≤ 65 years or >65 years) and Eastern Cooperative Oncology Group (ECOG) performance status (PS) of 0 vs 1 or 2. Study ended when the last subject enrolled completed the Week 24 tumor assessments or discontinued study drug before Week 24. Subjects received study treatment until disease progression, development of unacceptable toxicity, subject requested to discontinue, withdrew consent or was lost to follow-up, end of the study, or until study termination by the sponsor. After PD was observed, subjects were followed for PFS2 and survival.

This study consisted of 2 phases: the Prerandomization/Pretreatment Phase and the Randomization/Treatment Phase (see Figure 1). The Schedules of Procedures and Assessments for both study phases are explained in Table 7 of Protocol Amendment 05. Per protocol, tumor assessments were performed during the Prerandomization Phase and then every 8 weeks (within the 8th week) from the date of randomization during treatment cycles in the Randomization Phase. Subjects who discontinued treatment without PD in the Randomization Phase continued to undergo tumor assessments every 8 weeks until PD was documented or another anticancer therapy was initiated. Subjects were then followed every 12 weeks (± 1 week) for survival, PFS2 and all subsequent anticancer treatments received (unless this information was not allowed to be provided due to confidentiality) had been recorded until the End of Study.

[figure not shown]

Figure 1. Study Design for Study E7080-G000-211 (as of Protocol Amendment 05)

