5.4 Efficacy Analyses

5.4.1 Primary Efficacy Analyses

The noninferiority analysis of ORR_{24wk} between lenvatinib starting doses of 24 mg and 18 mg will be performed at the 1-sided alpha of 0.025, based on the calculated odds ratio of ORR_{24wk} response (18 mg vs 24 mg) along with its 95% confidence interval (CI) using the Cochran-Mantel-Haenszel (CMH) method, stratified by the randomization stratification factors. The test will be performed per the 95% CI using the noninferiority margin of 0.4. Noninferiority will be declared if the lower limit of the 95% CI for the odds ratio is greater than 0.4.

The point estimate of ORR_{24w} for each group will be summarized with the corresponding 95% CI using asymptotic normal approximation. Treatment difference (18 mg minus 24 mg) will also be estimated with its 95% CI using asymptotic normal approximation.

SENSITIVITY ANALYSIS

A sensitivity analysis will be performed for overall ORR using the same methods as used for ORR_{24wk} .

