5.4.2 Secondary Efficacy Analyses

- The following analyses will be performed on PFS, and censoring rules are detailed in [Section 8.4](#):
 - The difference in PFS between lenvatinib starting dose of 24 mg and 18 mg using stratified log-rank test with the randomization stratification factors, tested at an alpha level of 0.05
 - The estimate of the hazard ratio calculated from Cox proportional hazard model on PFS with lenvatinib starting dose as the independent variable and stratified by the randomization stratification factors with a 2-sided 95% CI
 - Kaplan-Meier (KM) estimated quartiles of PFS and their 95% CIs (using the generalized Brookmeyer and Crowley method) per lenvatinib starting dose
 - KM estimated PFS rates at 6, 12, 18 and 24 months and their 95% CIs (using Greenwood log-log formula) per lenvatinib starting dose
 - KM plot of estimated PFS over time

- The analyses of PFS will be repeated for PFS2, and the censoring rule is detailed in [Section 8.4](#)

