5.4.3 Other Efficacy Analyses

Duration of response (months), defined as the time from the initial achievement of a response (CR or PR) to the date of first documentation of PD or the date of death, whichever occurs first. It will be summarized for subjects with BOR of CR or PR.

For both endpoints, the censoring rules are the same as those for PFS censoring, when applicable. KM estimated quartiles and their 95% CIs per lenvatinib starting dose, using the generalized Brookmeyer and Crowley method, will be provided.

DCR and CBR will be evaluated using the same method as that used for ORR_{wk24} .

OS will be evaluated using the same method as that used for PFS, and censoring rule is detailed in [Section 8.4](#).

In addition, waterfall plots will be presented by lenvatinib starting dose for the percentage changes from Baseline to postbaseline nadir value in the sum of diameters of target lesions.

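### Minor, optional: the primary safety difference (Grade 3+ TEAEs by Week 24) has only a crude 95% CI; an interval stratified by the randomisation factors would be slightly narrower if those factors predict the event

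*SAP*

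**What the plan says.** Both documents describe stratified randomisation: "Subjects will be stratified by age" (protocol 9.4.3) and "Randomization was stratified by age" (SAP 3.2). The factors are age (65 or under, over 65) and ECOG PS (0, or 1 or 2), which give four strata.

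The SAP uses these strata for the main efficacy comparisons:

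- ORR24wk odds ratio (SAP 5.4.1): "Cochran-Mantel-Haenszel (CMH) method, stratified by the randomization stratification factors".
- PFS (SAP 5.4.2): "using stratified log-rank test with the randomization stratification factors", with a stratified Cox model. The same analyses are repeated for PFS2.
- OS (SAP 5.4.3): "OS will be evaluated using the same method as that used for PFS".

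The rate of Grade 3 or higher TEAEs within 24 weeks is listed as a primary endpoint beside ORR24wk (SAP 5.1.1). Its analysis in SAP 5.6.2 is the number and percentage per arm, and "the difference in frequency between the treatments (18 mg minus 24 mg) will be presented with 95% CI, using asymptotic normal approximation". Protocol 9.7.1.8.1 says "the difference in the frequency between the 2 treatment groups will be presented with 95% CI", and the synopsis says "the difference in the frequency between the 2 treatment groups will also be presented with 95% CI". None of the three names strata, and the protocol does not name a CI method.

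No other section supplies a stratified estimate. SAP 5.3.2 marks covariate adjustment as not applicable. The safety sensitivity analyses in protocol 9.7.1.8.3 follow the primary safety approach.

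**The concern.** When randomisation is stratified, the arms are balanced on the stratifying factors by design. If those factors predict the outcome, the difference between arms varies less from trial to trial than the crude standard error assumes. The crude interval is then somewhat wide. A stratified interval takes account of the balance.

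This endpoint carries the safety half of the primary objective. It has no test or success threshold, and the plan describes its adequacy by the width of this interval. An exploratory comparison (OS) therefore uses the strata while one of the two primary endpoints does not. At stake is a modest amount of reported precision, available from baseline data already collected.

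**Working it through.** **Inputs from the documents** (SAP 4; protocol 9.7.2): Grade 3+ TEAE rate at 24 mg in Study 303 of 70.5%; 76 subjects per arm; stated half-width of the 95% CI about 15 points.

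**Inputs the documents do not give:** event rates by age or ECOG PS, stratum sizes and block size. Everything below that uses strata is an assumption and is shown as a range.

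**1. The plan's own figure.** With 70.5% in both arms:

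1.96 × √(2 × 0.705 × 0.295 / 76) = 0.145, or 14.5 points.

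If the 18 mg rate is 65.5%, the half-width is 14.8 points; at 50.5% it is 15.2. The stated figure of about 15 is reproduced.

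**2. Stratified half-width.** With stratum shares w and rates p:

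1.96 × √(2 × Σ w·p(1−p) / 76).

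Assume that each factor has the same odds ratio (OR) for the event, that the effects add on the logit scale, and that the overall rate is fixed at 70.5%.

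| OR per factor | Stratum rates, equal strata (%) | Half-width, equal strata | Narrower by | Half-width, 60/40 split on both factors | Narrower by |
|---|---|---|---|---|---|
| 1 | 70.5 in all | 14.5 | 0% | 14.5 | 0% |
| 1.5 | 61.8, 70.8, 70.8, 78.5 | 14.4 | 0.8% | 14.4 | 0.8% |
| 2 | 55.6, 71.5, 71.5, 83.4 | 14.2 | 2.4% | 14.2 | 2.2% |
| 3 | 47.3, 72.9, 72.9, 89.0 | 13.7 | 5.5% | 13.8 | 4.9% |

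Worked example, OR 2 with equal strata: the mean of p(1−p) is 0.198, against 0.208 for the crude variance. 1.96 × √(2 × 0.1983 / 76) = 0.1416.

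**3. Coverage.** Simulation of 40,000 trials per case: 152 subjects, random stratum sizes with equal expectation, permuted blocks of 4, no true difference. The crude Wald interval is compared with the Mantel-Haenszel risk difference with Sato variance. The Monte Carlo standard error is 0.11 points.

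| OR per factor | Crude coverage | Stratified coverage |
|---|---|---|
| 1 | 94.7% | 94.6% |
| 1.5 | 94.9% | 94.6% |
| 2 | 95.1% | 94.6% |
| 3 | 96.0% | 94.7% |

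Repeat simulations of this setting put the stratified interval between about 94.5% and 94.9%. Both estimates are unbiased (error below 0.1 point). Mean simulated half-widths, crude against stratified, were 14.40 and 14.40 at OR 1, and 14.40 and 13.60 at OR 3.

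**4. Effect on the conclusion.** A separate simulation of 6,000 trials per case assumed stratum shares of 33/22/27/18%, with each factor raising risk by 0 to 15 points. With a true reduction of 15 points, the chance that the interval lies wholly below zero was 50.3 to 50.7% crude and 50.4 to 52.0% stratified. The standard deviation of the two estimates was almost identical (for example 7.21 points for both at 10 points per factor with no true difference). The difference therefore lies in the reported width, not in a better point estimate.

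**The case against.** The strongest reply is that nothing here is wrong, and that is correct. A reader might infer from the missing strata that the crude interval is biased or invalid, or that it misses the planned precision. The documents do not support either reading. The design asks for about 15 points and the crude interval gives 14.5, so it is not wider than the plan requires.

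A reader might also infer that the SAP is internally inconsistent. It does follow a recognisable convention. The ORR24wk percentage-point difference is crude as well (SAP 5.4.1), as are the differences in durable SD, DCR and CBR in protocol 9.7.1.6.3. What remains is that the ORR24wk difference accompanies a stratified odds-ratio test, while the safety difference has no stratified counterpart.

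Three further objections stand in part:

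- **The gain is assumed.** No section says that age or ECOG PS predicts Grade 3+ TEAEs, and OR 3 on both factors implies rates from 47% to 89% across strata. The lower part of the range, including zero, must be taken seriously.
- **Coverage is not improved throughout.** At OR 1.5 and 2 the crude interval is already close to 95%, because its overstated variance offsets the usual Wald shortfall, and the stratified interval is about 0.4 points under. Clear over-coverage of the crude interval appears only at OR 3. The change is free in data and subjects, but some of the narrowing is paid for in coverage.
- **No decision rule depends on it.** The safety comparison is an estimate with a CI, without a margin or threshold.

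These points reduce the matter to an optional improvement. They do not remove it: the interval is the whole inference for this endpoint, and there is no loss of width if the strata turn out not to matter.

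**Conclusion.** The point holds as a minor, optional improvement in precision and not as an error. The primary safety difference is planned with a crude interval only, although the strata are already used for the ORR24wk odds ratio, PFS, PFS2 and OS. The crude interval is valid and meets the stated half-width.

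Stratifying would narrow it by 0 to about 2.4% at odds ratios of 1 to 2 per factor (at most about 0.3 points on 14.5), and by up to about 5.5% (0.8 points) at an odds ratio of 3. Coverage would be about 0.1 to 0.5 points under 95%. These sizes rest on assumed stratum rates, stratum shares and block size. The safety conclusion is unlikely to change.

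**What to change.** In SAP 5.6.2, before unblinding, specify the risk difference (18 mg minus 24 mg) with Mantel-Haenszel weights over the four age by ECOG PS randomisation strata, and a matching stratified 95% CI, for example with the Sato variance. Keep the Safety Analysis Set and the as-treated arms. State that a stratum with no subjects in one arm gets zero weight; the weight n1·n0/(n1+n0) already gives this. Keep the number and percentage per arm, and keep the crude difference with its CI as supportive. Use the same method for the safety sensitivity analyses in protocol 9.7.1.8.3. Record the change in SAP section 7.

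The cost is a few sentences and one extra estimate from data already collected. Sample size, endpoint and analysis set do not change. No protocol amendment is needed, because protocol 9.7.1.8.1 asks for a 95% CI without fixing the method.
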